6.3 Prohibited treatments

The following treatments are not allowed **during emapalumab treatment**:

- Methylprednisolone more than 2 mg/kg/day (or other equivalent steroid dose) for more than 2 days.

The following treatments are not allowed during **monitoring/extended monitoring and during emapalumab treatment**:

- All kinase inhibitors.
- Interferon gamma-1b.
- Biologic drugs (except rituximab used to treat EBV infection or to remove B-cells producing donor specific antibodies).

The following treatments are not allowed **during the study up to 6 months after the last emapalumab dose or until the end the monitoring period for untreated patients**:

- Live or attenuated (including BCG) vaccine.

7 STUDY END POINTS

The main objective is dual and is composed of:

- Dose selection.
- Preliminary efficacy of emapalumab treatment pre-empting GF.

The endpoints used to assess dose selection are:

- Serum concentrations of free emapalumab.
- Serum concentration of total IFN γ .
- Serum concentration of CXCL9.

The main endpoint used to preliminarily assess efficacy of emapalumab in pre-empting GF is:

- Occurrence of primary GFs from start of treatment up to end of treatment.

7.1 Efficacy

- Occurrence of primary GF from HSCT up to EoS visit.
- Occurrence of secondary GF from HSCT up to EoS visit.
- Occurrence of primary or secondary GFs from HSCT up to EoS visit.
- Occurrence of mixed donor chimerism <10% and <20% (based on unselected leukocytes or sorted T cells) from HSCT up to EoS visit.
- Occurrence of received transfusion of blood products due to poor graft function, hematopoietic growth factors, stem cell boost or DLI from HSCT up to 3 years follow up.
- Occurrence of receiving an additional allogeneic HSCT from HSCT up to 3 years follow up.
- Occurrence of poor graft function from HSCT up to EoS visit.
- Occurrence of event free engraftment from HSCT up to 3 years follow up.
- Occurrence of GvHD from HSCT up to 3 years follow up.
- Occurrence of engraftment syndrome from HSCT up to EoS visit.
- Occurrence of endothelial complications from HSCT up to EoS visit.
- Overall survival from HSCT up to 3 years follow up.

7.2 Safety

- Occurrence of relapse, defined as cumulative incidence of reoccurring malignant underlying disease from HSCT up to EoS visit.
- Occurrence of AEs up to EoS visit.
- Occurrence of AEs leading to discontinuation of study treatment.
- Change from baseline in vital signs, laboratory parameters up to EoS visit.

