3.4.5 Follow-Up Period

Assessments to be performed during the follow-up period are detailed in the Schedule of Assessments (Table 7a and Table 7b). The follow-up period will last 3 years from the HSCT date for both patients who received and those who did not receive emapalumab, as detailed below.

Follow-up period: emapalumab treated patients

All emapalumab treated patients will enter the follow-up period:

- (i) Upon completion of treatment or engraftment, whichever comes first
- (ii) In case of premature treatment discontinuation for any reason

The follow-up period for patients who received emapalumab will consist of 6 visits: at 1 week \pm 2 days, 2 weeks \pm 2 days, 4 weeks \pm 2 days, 8 weeks \pm 1 week, 12 weeks \pm 1 week and 24 weeks \pm 2 weeks after last study drug administration (EoS visit) and 3 phone calls for survival observation at 1, 2 and 3 years after HSCT.

During the survival calls defined concomitant medications/procedures (i.e. any HSCT, blood product transfusion, stem cell boost, DLI or hematopoietic agents) and occurrence of GvHD since previous visit/call should be recorded.

The first follow-up visit will be 1 week \pm 2 days after last study drug administration or 1 week after EoT (in case of treatment discontinuation or engraftment before the last dosing day).

Follow-up period: non-emapalumab treated patients

In case treatment with emapalumab has not been initiated, patients will undergo an EoS visit (within 1 week from the last day in the monitoring periods) and enter the phone calls follow-up.

A patient can enter follow-up in the following occasions:

- (i) At the end of the monitoring (Day 42) or extended monitoring (Day 98).
- (ii) If they require a second HSCT anytime during the monitoring periods.
- (iii) If any prohibited medication is taken during the monitoring periods.
- (iv) In case of re-occurrence of malignant disease, GvHD diagnosis, uncontrolled infection or clinical manifestations of infections representing exclusion criteria at time of eligibility to treatment.

The follow-up period for non-emapalumab treated patients will consist of 4 phone calls at 6 months, 1, 2 and 3 years after HSCT. During the survival calls defined concomitant medications/procedures (i.e. any HSCT, blood product transfusion, stem cell boost, DLI or hematopoietic agents) and occurrence of GvHD since previous visit/call should be recorded.

End of Study Visit

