Assessments to be performed during the EoS visit are detailed in the Schedule of Assessments (Table 7a and Table 7b).

- For emapalumab treated patients, the EoS visit correspond to the last follow-up visit (Follow-up visit 6) at week 24 \pm 2 days from last study drug administration.
- Non-emapalumab treated patients will require to attend the EoS visit within 1 week from the last day in the monitoring periods.

Table 2 Transition between periods in case of ANC < 500 cells/ μ L during the monitoring period

Monitoring	Treatment	Follow-up For emapalumab treated patients	Follow-up For non-emapalumab treated patients
CXCL9 above threshold + ANC <500 cells/ μ L 	Enter treatment period		Perform EoS visit and enter phone-calls follow-up period:
CXCL9 below threshold + ANC <500 cells/ μ L  Continue monitoring ✓ Unless a second HSCT is required ✓ As soon as ANC \geq 500, transition to extended monitoring Table 3		Enter follow-up period: ✓ Upon completion of treatment or engraftment during treatment, whichever comes first ✓ Upon premature treatment discontinuation for any reason	
 ✓ At the end of monitoring or ext monitoring period ✓ In case of re-occurrence of malignant disease, GvHD diagnosis, uncontrolled infection or clinical manifestations of infections representing exclusion criteria at time of treatment ✓ If a second HSCT is required ✓ If any prohibited med is taken during the monitoring periods

Table 3 Transition between periods in case of ANC \geq 500 cells/ μ L during the monitoring period

Monitoring	Extended Monitoring	Treatment	Follow-up For emapalumab treated patients	Follow-up For non-emapalumab treated patients
As soon as ANC \geq 500 cells/ μ L during monitoring, enter extended monitoring	CXCL9 above threshold + Signs of sGF 	Enter treatment period	Enter follow-up period: ✓ Upon completion of treatment or engraftment during treatment, whichever comes first	Perform EoS visit and enter phone-calls follow-up period: ✓ At the end of monitoring or ext monitoring period ✓ In case of re-occurrence of malignant disease, GvHD diagnosis, uncontrolled infection or clinical manifestations of infections representing exclusion criteria at time of treatment
	If CXCL9 below threshold Continue extended monitoring unless a second HSCT is required		✓ Upon premature treatment discontinuation for any reason	
 ✓ If a second HSCT is required ✓ If any prohibited med is taken during the monitoring periods

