10: Free IFN γ (pre-dose only before dose 1) and total IFN γ , CXCL9 and other inflammatory biomarkers in serum (e.g. IL-6, TNF α , Scd163 and Sil2R α).	

Table 7a: Schedule of assessments - Follow-up period, withdrawal visit, EoS and unscheduled visit (Cohort 1, 2 and 3) - Patients weight \geq 30 kg

PERIOD (Duration)	FOLLOW UP ¹ (3 years)											Unscheduled Visit ⁴
	FU 1 ¹	FU 2 ¹	FU 3 ¹	FU 4 ¹	FU 5 ¹	FU6 ¹ or EoS visit ^{1,2} or Withdrawal visit ³	Phone calls					
Days \pm window	Week 1 \pm 2 days	Week 2 \pm 2 days	Week 4 \pm 2 days	Week 8 \pm 1 week	Week 12 \pm 1 week	Week 24 \pm 2 Weeks	6 months \pm 2 weeks from HSCT ²	1 year \pm 4 week from HSCT ^{1,2}	2 year \pm 4 weeks from HSCT ^{1,2}	3 year \pm 4 Weeks from HSCT ^{1,2}		
Clinical Assessments	Vital Signs (BP, HR, body temperature)	X	X	X	X	X	X					X
	12-lead ECG											(X)
	Chest X-ray	Only in case of clinical suspicion of pulmonary infection					X					(X)
	Physical Examination	As medically required					X					X
	Weight	X	X	X	X	X	X					X
	Record engraftment syndrome			X	X	X	X					(X)
Laboratory Procedures	Record GvHD, GF, graft rejection	X	X	X	X	X	X					(X)
	Biochemistry and hematology including differential haematology ⁵	X		X	X	X	X					(X)
	Re-occurrence or progression of underlying malignant disease (MRD)			X	X	X	X					(X)
	Urine Pregnancy Test (if applicable)			X	X	X	X					(X)
	Urinalysis	X	X	X	X	X	X					(X)
	Search for infections ⁶	If an infection is suspected										(X)
	TB testing						X					(X)
	Cells subsets			X		X	X ⁸					(X)
	Donor chimerism			X	X	X	X					(X)
	Inflammatory biomarkers ⁷	X	X	X	X	X	X					(X)
	HLA antibodies against donor cells						X					(X)
	PK			X	X	X	X ⁸					(X)
	Antibodies against emapalumab			X		X	X ⁸					(X)
Survival check and GvHD occurrence recording											X	(X)
Relevant concomitant medications/procedures⁹	X										X	X
AEs	X										Only SAEs related to emapalumab	X

Table 7a Foot Notes
Abbreviations: FU: Follow Up; EoS: End of Study visit; BP: Blood Pressure; HR: Heart Rate; ECG: Electrocardiogram; MRD: Minimal Residual Disease; GF: Graft Failure; GvHD: Graft versus Host Disease; HLA: Human Leukocyte Antigen PK: pharmacokinetics; AEs: Adverse Events
1: This visit is foreseen for emapalumab treated patients. FU week 1 to be scheduled 1 week \pm 2 days from last study drug administration or 1 week after EoT (in case of treatment discontinuation or engraftment before the last dosing 15).

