2: This visit is foreseen for non-emapalumab treated patients. The EoS visit for non-emapalumab treated patients must be scheduled within 1 week from the last day in the monitoring periods.
3: In case of premature withdrawal from the study for any reason (except informed consent withdrawal), patients should undergo a withdrawal visit within 1 week from the date of withdrawal.
4: Assessments marked as (X) will be done if considered medically relevant
5: Biochemistry: Glucose, C-reactive protein (CRP), Sodium, Potassium, Chloride, Calcium, Magnesium and Phosphate, AST, ALT, γ GT, ALP, LDH, bilirubin (total, direct and indirect), triglycerides, cholesterol (total and HDL), Albumin, creatinine, urea (fasting conditions whenever possible), Ferritin. Hematology: hematocrit, hemoglobin, platelets, RBC, WBC. Hematology differential: lymphocytes, monocytes, neutrophils.
6: Atypical mycobacteria, salmonella, histoplasma capsulatum, herpes zoster, HHV6, CMV, EBV, adenovirus, parvovirus.
7: Total IFN γ , CXCL9 and other inflammatory biomarkers in serum (e.g. IL-6, TNF α , sCD163 and sIL2R α)
8: this sample is collected for emapalumab treated patients only
9: Relevant procedures /medications are defined as any HSCT, blood product transfusion, stem cell boost, DLI or hematopoietic agents received since the previous visit/call.

Table 7b: Schedule of assessments – Follow-up period, withdrawal visit, unscheduled visit (Cohort 1, 2 and 3) - Patient weight < 30 kg

PERIOD (Duration)		FOLLOW UP (3 years)										Unscheduled Visit ⁴	
		FU 1 ¹	FU 2 ¹	FU 3 ¹	FU 4 ¹	FU 5 ¹	FU6 ¹ or EoS visit ^{1,2} or Withdrawal ³	Phone calls					
Days ± window		Week 1 ±2 days	Week 2 ±2 days	Week 4 ±2 days	Week 8 ±1 week	Week 12 ±1 week	Week 24 ±2 Weeks	6 months ±2 weeks from HSCT ²	1 year ±4 week from HSCT ^{1,2}	2 year ±4 weeks from HSCT ^{1,2}	3 year ±4 Weeks from HSCT ^{1,2}		
Clinical Assessments	Vital Signs (BP, HR, body temperature)	X	X	X	X	X	X					X	
	12-lead ECG											(X)	
	Chest X-ray	Only in case of clinical suspicion of pulmonary infection					X						(X)
	Physical Examination	As medically required					X						X
	Weight	X	X	X	X	X	X						X
	Record engraftment syndrome			X	X	X	X						(X)
Laboratory Procedures	Record GvHD, GF, graft rejection	X	X	X	X	X	X					(X)	
	Biochemistry and hematology including differential haematology ⁵	X		X	X	X	X					(X)	
	Re-occurrence or progression of underlying malignant disease (MRD)			X*	X*	X*	X					(X)	
	Urinalysis	X	X	X	X	X	X					(X)	

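### Relapse and AEs are counted to an End of Study visit that falls months later for treated than for untreated patients, and the later calls do not ask about relapse

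*Combined protocol and SAP*

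**What the plan says.** Section 7.2 of the protocol defines the relapse endpoint as "Occurrence of relapse, defined as cumulative incidence of reoccurring malignant underlying disease from HSCT up to EoS visit". AEs are counted to the same visit (Sections 7.2 and 9.1.4).

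Section 3.4.5 places that visit differently by group. "For emapalumab treated patients, the EoS visit correspond to the last follow-up visit (Follow-up visit 6"), which is 24 weeks after the last dose. By contrast, "Non-emapalumab treated patients will require to attend the EoS visit within 1 week from the last day in the monitoring periods".

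Section 12.4 uses all included patients, treated or not, for safety endpoints. Section 12.5 presents data by dose regimen, total emapalumab group and untreated group, with counts and percentages for categorical variables.

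In Table 7a the row "Record GvHD, GF, graft rejection" and the MRD row apply to visits, not to the scheduled calls. The calls carry "Survival check and GvHD occurrence recording", an AE entry limited to "Only SAEs related to emapalumab", and named procedures and medications, which footnote 9 defines as "any HSCT, blood product transfusion, stem cell boost, DLI or hematopoietic agents received since the previous visit/call". Relapse is not among the items. Table 7b is the same in these respects.

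**The concern.** Two things follow if the plan is carried out as written. First, treated and untreated relapse or AE percentages would describe different lengths of time after transplant. Second, relapse after EoS would not be systematically collected in either group, even though calls continue to three years.

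Relapse is the safety outcome for a risk that the protocol itself names. Section 10.2.4 describes the effect of emapalumab in malignant disease as unknown and says that neutralizing IFNγ may weaken graft-versus-tumor activity. Untreated patients are the only in-study background for relapse, and the CSR uses data up to EoS (Section 12.2). A reader of the CSR could not tell how much of any relapse difference, in either direction, came from the window.

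**Working it through.** **1. The plan's own figure.** Dose 2 is 3 days after dose 1, and the other 13 doses follow every 3 or 4 days (Section 5.4). Dose 15 is therefore 3 + 13×3 = 42 to 3 + 13×4 = 55 days after dose 1. Counting the first day, that is 56 calendar days, which reproduces the stated maximum.

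**2. EoS in days from HSCT** (visit windows ignored; Day 42 and Day 98 as in Section 3.4.5):

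| Group | Calculation | EoS |
|---|---|---|
| Treated for primary GF, earliest | 1 + 0 + 168 | Day 169 |
| Treated for primary GF, latest | 42 + 55 + 168 | Day 265 |
| Treated for secondary GF, latest | 98 + 55 + 168 | Day 321 |
| Untreated, monitoring only | 42 + 7 | Day 49 at latest |
| Untreated, extended monitoring | 98 + 7 | Day 105 at latest |

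Untreated patients who leave early, or who are moved on at a cohort hold (Section 3.3), reach EoS sooner. Measured from HSCT, AE collection is 169/105 = 1.6 to 265/105 = 2.5 times as long after treatment for primary GF as for an untreated patient who completes extended monitoring.

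**3. Effect on relapse percentages with no drug effect.** The documents give no relapse rate or hazard shape, so both are assumptions. Let r be the one-year risk and S(t) = (1−r)^((t/365)^k), where k = 1 is a constant hazard and k = 0.5 a front-loaded one. Untreated: 1 − S(105). Treated patients must be free of recurrence at first dose (Section 3.4.3), so with first dose on day s the figure is 1 − S(s+L)/S(s). Here L = 168 to 168 + 55 = 223 days.

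For r = 20%:
- k = 1: untreated 1 − 0.8^0.2877 = 6.2%. Treated 1 − 0.8^0.4603 = 9.8% to 1 − 0.8^0.6110 = 12.7%, for any s.
- k = 0.75, s = 42: untreated 8.4%; treated 9.8-12.3%.
- k = 0.5, s = 42: untreated 1 − 0.8^0.5363 = 11.3%. Treated 1 − 0.8^(0.7585−0.3392) = 8.9% to 1 − 0.8^(0.8521−0.3392) = 10.8%.

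At k = 0.5 the order reverses once the first dose falls after about Day 10 (L = 168) or Day 33 (L = 223).

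For r = 10%: 4.7-6.2% against 3.0% (k = 1), and 4.3-5.3% against 5.5% (k = 0.5, s = 42). For r = 30%: 15.1-19.6% against 9.8%, and 13.9-16.7% against 17.4%.

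**4. Relapse after EoS in untreated patients, Day 105 to one year.** The share is S(105) − S(365). For r = 20% it is 13.8% (k = 1), 11.6% (k = 0.75) or 8.7% (k = 0.5).

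At the 250-patient maximum, 18 evaluable patients are treated for primary GF (3×4 + 6), with up to a similar number for secondary GF. That leaves 214 to 232 untreated. If 40-60% have malignant disease (the screening strata, assumed to carry over), that is 214×0.4 = 85.6 to 232×0.6 = 139.2 patients. The number of relapses is 11.8-19.2, 9.9-16.2 or 7.46-12.1 for the three shapes, so about 7-19. Across r = 10-30% and all shapes the range is 3.9 to 28.2, about 4-28. Deaths are ignored.

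If the study stops at 7 evaluable patients in cohort 1, 7/0.3 = 23 to 7/0.1 = 70 patients are included and 7-14 treated. At r = 20% the number is 0.3-1.3 (23 included) or 2.0-5.2 (70 included), so about 0-5.

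**5. Detection.** For patients of 15 kg or more, MRD is scheduled six times if treated (dose 1, dose 11 or an earlier EoT, follow-up weeks 4, 8, 12 and 24) and once if untreated (EoS).

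**The case against.** The study is single-arm, every analysis is declared exploratory, and no treated-versus-untreated relapse comparison is planned. The groups differ by CXCL9 by design, so equal windows would not make them comparable. Long follow-up of treated patients tracks exposure: 168 days is about 7.6 half-lives of 22 days (168/22), and untreated patients have no exposure to follow. Section 12.5 leaves full detail to the SAP, no separate SAP text was available for this review, and Section 7.2 already speaks of cumulative incidence. Clinical relapse before EoS can be recorded in both groups, so the MRD count overstates unequal detection.

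Most of this stands. It limits the point to descriptive displays and makes criticism of the estimator conditional on the SAP. It does not answer the collection gap: a SAP can set a common day, but it cannot recover relapses that no form asked about.

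A reader might infer that the safety percentages are uninterpretable and that late relapse is lost. The documents do not support that. Within-group description remains valid if follow-up time is shown, and in treated patients a relapse judged an emapalumab-related SAE is still reported after EoS (Section 9.2.2).

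A reader might also infer that late GF is lost. That is a minor point. Section 10.1 calls a second transplant the only treatment for confirmed GF, and additional HSCT, boost, DLI and survival are recorded to three years. Most late GF would therefore surface, though not dated as GF.

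**Conclusion.** The point holds as a cheap improvement. Unequal EoS days alone would make crude relapse and AE percentages differ between the displayed groups, and relapse after EoS is not systematically captured in either group.

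It is tempting to conclude that treated patients will look worse. For relapse the direction cannot be fixed in advance. It depends on the hazard shape and the day of first dose, and recurrence at the time of treatment eligibility moves a patient into the untreated group. Nor can the distortion be stated as a bounded number of treated patients. The figure of 18 counts only evaluable primary-GF patients, and the malignant/non-malignant strata are set at screening, not among those treated.

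The day arithmetic follows from the protocol. The percentages and patient counts rest on assumed relapse risks of 10-30% and assumed hazard shapes. The counts also rest on an assumed malignant share of 40-60% among untreated patients. Dose selection, the main efficacy endpoint, overall survival, GvHD and additional HSCT are unaffected.

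**What to change.** 1. Add one dated relapse item, for malignant disease only, to the existing 1-, 2- and 3-year calls for all patients and to the untreated patients' 6-month call. A dated GF item is optional.
2. Wherever treated and untreated relapse appear together, report cumulative incidence at a common day from HSCT, for example one year, with death as a competing event and censoring at last contact. Describe treated patients also from first dose. Do not rely on a Day 98 estimate with delayed entry: the treated group is small, and a patient first dosed near that day adds almost nothing to it.
3. Show recurrence found by MRD alone separately from clinical relapse.
4. State follow-up time by group beside AE percentages.

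No new visits or samples are needed. The cost is an eCRF change and SAP wording, probably a protocol amendment with IRB/IEC approval (Section 13.6), possible re-consent (Section 13.4) and a little site time per call. Late events would rest on report rather than scheduled assessment.

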- If CXCL9 is measured below threshold, patients will continue the extended monitoring period until Day 98 \pm 3 days or until a second HSCT is planned.

Criteria not to start treatment during monitoring or extended monitoring

Patients presenting the following conditions at time of initiation of emapalumab treatment will not be eligible to receive emapalumab and will move to the phone-call follow-up period for non-emapalumab treated patients (see section 3.4.5).

- Uncontrolled infections (defined as clinically active infection regardless of treatment).
- Clinical manifestations of infections representing exclusion criteria (i.e. Atypical mycobacteria, Salmonella, Histoplasma capsulatum, Herpes zoster).
- Re-occurrence or progression of the underlying malignant disease based on medical judgment.
- GvHD.

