8.3.4 Post-HSCT clinical assessments

Several clinical assessments are performed post-HSCT during monitoring, treatment and follow up. These assessments are reported in the assessment schedule under clinical assessments from Table 5a to Table 7b.

- Monitoring of occurrence of GvHD and/or engraftment syndrome, graft failure and graft rejection will be assessed during the monitoring, extended monitoring, treatment and follow-up period. Information on the severity and clinical characteristics of GvHD, engraftment syndrome, graft failure and graft rejection (in case of occurrence) will be collected in the eCRF.
- Re-occurrence or progression of the underlying malignant diseases will be monitored prior to treatment initiation, during treatment and follow-up period as indicated in the assessment schedule. Re-occurrence or progression of the disease will be assessed by measuring the minimal residual disease (MRD) in patients with malignant underlying disease.

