11.1.2 Emapalumab permanent discontinuation

Study drug must be permanently discontinued in the following situations:

- Any treatment emergent adverse reaction (i.e. assessed as related), which is considered as life-threatening.
- Any medical condition that the Investigator or Sponsor determines may jeopardize the subject's safety.
- Re-occurrence of malignant disease as judged by the investigator based on clinical assessment including MRD monitoring.

In the situations described above, IDMC will be promptly informed and involved in evaluation of the patient's data.

Other situations that must lead to treatment permanent discontinuation are:

- Pregnancy.
- If a re-transplant is needed based on medical judgment.
- Graft failure.

The reason for study treatment discontinuation should be documented as appropriate in the eCRF.

The Investigator can decide at any time during the study to discontinue the treatment in a patient based on medical judgment, taking into account the benefit/risk ratio for continuing the treatment.

Decision to discontinue treatment will have no impact on the patient's care. All patients who discontinue treatment will be treated according to local medical practice. A subject who prematurely discontinues study treatment is NOT considered as withdrawn from the study. All assessments relevant to EoT visit must be performed and the patient will enter the follow-up period.

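### Relapse rates for treated and untreated patients cannot be read side by side: scheduled MRD draws, the date of EoS and entry to the groups all depend on treatment status

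*Combined protocol and SAP*

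**What the plan says.** **Endpoint and display.** Section 7.2 defines the endpoint as "Occurrence of relapse, defined as cumulative incidence of reoccurring malignant underlying disease from HSCT up to EoS visit". Section 12.4 uses the all included population, treated or not, for safety endpoints. Section 12.5 presents data by dose regimen, total emapalumab group and untreated group, and calls all analyses exploratory.

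**Detection.** Section 8.3.4: "Re-occurrence or progression of the disease will be assessed by measuring the minimal residual disease (MRD) in patients with malignant underlying disease". Tables 5a and 5b (screening, HSCT, monitoring, extended monitoring) have no MRD row. Tables 6a to 7b place the draws in the treatment and follow-up periods. Elsewhere the standard is wider: section 11.1.2 stops the drug on "Re-occurrence of malignant disease as judged by the investigator based on clinical assessment including MRD monitoring".

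**Window.** Section 3.4.5: "For emapalumab treated patients, the EoS visit correspond to the last follow-up visit (Follow-up visit 6) at week 24" after the last dose. For the others: "Non-emapalumab treated patients will require to attend the EoS visit within 1 week from the last day in the monitoring periods". In the later calls, survival, listed procedures and medications, and "occurrence of GvHD since previous visit/call should be recorded" are collected. Relapse is not on that list.

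**Entry.** Section 3.4.3 lists "Re-occurrence or progression of the underlying malignant disease based on medical judgment" among the conditions that bar the first dose. Such patients "will not be eligible to receive emapalumab and will move to the phone-call follow-up period for non-emapalumab treated patients".

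**The concern.** Section 10.2.4 says that the effect of emapalumab in malignant disease after allogeneic HSCT is unknown and that neutralising IFNγ may weaken graft-versus-tumour activity. Relapse is the endpoint that speaks to this risk, and at least 40% of patients are to have malignant disease.

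The tables will set a treated rate beside an untreated rate. If the groups are searched with different intensity, watched for different lengths of time, and sorted partly by whether relapse has already occurred, the two rates can differ with no drug effect, or agree when there is one. A reader planning the next study could be misled either way.

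**Working it through.** The plan gives no relapse rate, sample size or power for this endpoint, so there is no figure to reproduce. The check counts scheduled draws, derives the EoS days, and illustrates the effect of window length.

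**1. Scheduled MRD draws, malignant disease, follow-up completed**

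| | Treated | Untreated |
|---|---|---|
| 15 kg or more | dose 1; dose 11 (or EoT if before dose 11); FU3, FU4, FU5, FU6 = 6 | EoS = 1 |
| Below 15 kg (starred draws dropped) | FU6 = 1 | EoS = 1 |

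Taking the dose-1 draw as a pre-treatment reference leaves 5 against 1 at 15 kg or more.

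Example: doses on Days 10, 13, 17, 21, 25 and 29, engraftment about Day 30. Draws after the reference fall at EoT about Day 33, FU3 at 29 + 28 = Day 57, and FU4 at 29 + 56 = Day 85, so there are three by Day 98. An untreated patient who completes extended monitoring has one, at Day 98 to 105.

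**2. Day of EoS, counted from HSCT**

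Treated EoS = last dose + 24 × 7 = last dose + 168.
- Earliest: a single dose on Day 1 gives 1 + 168 = Day 169, or 169 − 14 = Day 155 with the two-week window.
- Dose 15 falls at latest on treatment day 3 + 13 × 4 = 55. Latest EoS for primary GF is 42 + 55 + 168 = Day 265; for secondary GF it is 98 + 55 + 168 = Day 321.

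Untreated EoS = last monitoring day + at most 7.
- No ANC recovery: 42 + 7 = Day 49 (43 + 7 = Day 50 with the window).
- Extended monitoring to Day 98 from HSCT, as in Table 1: 98 + 7 = Day 105 (101 + 7 = Day 108).
- Extended monitoring read as 98 days from its own start, which the wording of 3.4.3 and 8.4 permits: 42 + 98 + 7 = Day 147 (43 + 101 + 7 = Day 151).

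| Reading of extended monitoring | Gap, nominal | Gap, widest windows |
|---|---|---|
| To Day 98 from HSCT | 169 − 105 = 64 days | 155 − 108 = 47 days |
| 98 days from its own start | 169 − 147 = 22 days | 155 − 151 = 4 days |

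The ranges do not overlap under either reading. Section 3.3 shortens some untreated windows further, because patients in monitoring when screening is put on hold go straight to EoS.

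**3. What the window alone can do**

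Assume the same constant relapse hazard in both groups, h = −ln(1 − r)/365, with one-year risk r from 10% to 40% (an assumption; the plan gives no rate). Risk over t days is 1 − exp(−h·t). Take a treated patient with first dose on Day 14 and last dose on Day 42, so EoS is Day 210. Relapse-free at first dose, that patient has 210 − 14 = 196 days at risk.

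| r | Untreated to Day 49 | To Day 105 | To Day 147 | Treated, 196 days |
|---|---|---|---|---|
| 10% | 1.4% | 3.0% | 4.2% | 5.5% |
| 20% | 3.0% | 6.2% | 8.6% | 11.3% |
| 30% | 4.7% | 9.8% | 13.4% | 17.4% |
| 40% | 6.6% | 13.7% | 18.6% | 24.0% |

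The treated figure is about 3.6 to 3.9 times the Day 49 figure, about 1.8 times the Day 105 figure, and about 1.3 times the Day 147 figure, with no drug effect.

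**4. Direction of each difference**
- More draws raise the treated count, if MRD-only positivity counts as relapse.
- A longer window raises the treated count.
- The entry rule moves relapses found at treatment eligibility into the untreated group. It also makes treated time before first dose relapse-free by medical judgment, for up to 42 days (primary GF) or 98 days (secondary GF). It lowers the treated rate from HSCT and raises the untreated one.

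The documents give nothing from which to net these.

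**The case against.** **No comparison is planned.** This stands. The study is single arm and descriptive. Sections 3.2 and 10.1 give the untreated group other purposes: the frequency of GF when CXCL9 is below threshold, and CXCL9 as a biomarker. The CXCL9 and ANC trigger already separates the groups, so equal schedules would not create a control. A reader might infer that the plan makes an invalid drug comparison on relapse; it does not. What remains is that 12.5 puts the two rates in adjacent columns.

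**Cumulative incidence can handle unequal follow-up.** Partly right. With censoring at EoS it deals with window length. It does not deal with detection frequency or group entry. The sections on safety data and missing data (12.5.3 and 12.5.6) specify only descriptive summaries of observed data. Section 12.5 leaves full detail to a separate SAP, which may say more.

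**Detection is not MRD alone.** Also right. Investigator judgment counts in 3.4.3 and 11.1.2, MRD may be done at unscheduled visits, and AEs are collected to EoS in both groups. Closer MRD follow-up of dosed patients is deliberate risk minimisation. The 6 against 1 count is therefore of scheduled draws only. Discretionary testing does not make detection equal, and 7.2 and 8.3.4 do not separate MRD-only positivity from clinical recurrence.

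**A Day 98 main row would weaken the safety readout.** Correct. Secondary GF treatment can start as late as Day 98, so that row would hold little post-dose time for late-treated patients. The common window should be supplementary.

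**Conclusion.** The point holds as one about presentation and interpretation. By rule, treated and untreated relapse differ in scheduled MRD (6 against 1 at 15 kg or more, equal below), in date of EoS (no overlap on either reading of extended monitoring) and in entry to the groups. Neither a difference between the displayed rates nor its absence can be read as a drug effect.

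Four stronger conclusions are tempting but unsupported:
- **That relapse is biased against emapalumab.** The 1.3- to 3.9-fold figures isolate the window under an assumed constant hazard and one dosing example. The entry rule works the other way, and the net direction is uncertain.
- **That the windows are always 64 or 47 days apart.** On the other reading of extended monitoring the gaps are 22 or 4 days.
- **That the coarseness of the treated rate measures bias.** One event will move a rate in so small a group noticeably, but that is sample size and applies to every endpoint here.
- **That disease status at HSCT goes uncollected.** The eCRF is not part of the text, and inclusion criterion 3 already requires status for most of the malignancies.

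The counts assume malignant disease and completed follow-up.

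**What to change.** In 7.2 and the SAP, using data already collected:

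1. Keep treated relapse to EoS as the main safety row, counted from first dose with follow-up time shown. Late events and MRD signals stay in the safety readout.
2. Tabulate clinical or haematological recurrence separately from MRD-only positivity, with the dose-1 MRD as the pre-treatment reference. Recurrence can be taken from the AE data that 9.1.4 requires to EoS in both groups.
3. Wherever treated and untreated patients appear together, add a supplementary cumulative incidence of clinical recurrence over a common time from HSCT, about Day 98. Censor at EoS, show numbers at risk, count patients as untreated until first dose, and identify relapses that barred treatment under 3.4.3.
4. State beside the table that the groups are not a controlled comparison.

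The cost is a few table rows and some wording, with no new samples or visits. The common-window row will hold fewer events. It will also thin out after Day 42 to 49 as untreated patients without ANC recovery leave, which is why numbers at risk must be shown.
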